6.4 Handling of Missing Data

The analyses will initially focus on the study completers to estimate the effect of the brief behavioral intervention in patients with advanced lung cancer who completed the protocol as intended without imposing assumptions about missing data. We will also use the intention-to-treat principle with all randomized subjects, conducting sensitivity analyses to explore how various assumptions about missing data and differences between completers and non-completers affect the estimated outcomes. If data appear to be missing at random, we will employ multiple imputation methods. However, if we find that patients do not complete the study because of disease worsening, suggesting missing data are not random, we will employ maximum likelihood estimation from incomplete data, under the direction of our biostatistician, [name].

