5.4.2 Data from the Electronic Health Record

Clinical information regarding tumor type (NSCLC, SCLC, mesothelioma), date of diagnosis of advanced disease, previous cancer therapies, current treatment regimen, and performance status will be collected at baseline. The post study review of the electronic health record (EHR) will include information on disease progression, any changes in cancer treatment, and number of emergency department (ED) visits and hospitalizations during the study period.

Medical comorbidity will be assessed at the time of baseline data collection with the Charlson Comorbidity Index (CCI).⁶⁷ We will review health records for the presence of (1) pulmonary, cardiac, hepatic, and renal disease, (2) current and other malignancies, and (3) other morbidities (diabetes, cerebrovascular disease, and rheumatologic conditions) and assign the appropriate CCI score.

Medical orders: We will collect data on medications to alleviate dyspnea (e.g., opioid analgesics), supplemental oxygen, and procedures for managing pleural effusions or bronchial obstruction.

[name] (Co-I), a thoracic oncologist, will oversee the collection of clinical information from the EHR as well as the review of medical scans to determine whether participants'

disease progressed during the study period.

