6.3 Analysis Plan

6.3.1 Aim 1

Aim 1: To demonstrate the efficacy of the brief behavioral intervention for improving dyspnea (primary outcome) in patients with advanced lung cancer.

Hypothesis 1: Participants with advanced lung cancer who are randomly assigned to receive the brief behavioral intervention will report statistically and clinically significant improvements in dyspnea (per self-report MMRCDS and CDS) compared to those assigned to usual care.

Analysis: Analyses will begin with descriptive and graphical summaries of the endpoints. As the MMRCDS is an ordinal measure, the statistical significance of between-group differences in the primary outcome will be assessed first with the Wilcoxon-Rank Sum test and then with generalized estimating equations (GEE), with appropriate covariates. The CDS is a continuous interval measure, and we will assess between-group differences in these scores using general linear models (GLM). All statistical tests will be two-sided with an alpha level of .05. For these primary outcomes, we will examine between-group differences (i.e., intervention versus control) in MMRCDS and CDS scores at the 8-week post-assessment, controlling for baseline values. In the event that the effect of the intervention differs by cancer type, use of opiate medication or other patient characteristic, we will examine these variables as interaction terms in the GEE and GLM analyses. We will also evaluate generalized linear mixed models of the longitudinal data, allowing us to

account for dependency among MMRCDS and CDS scores over time and to control for demographic and clinical factors, such as disease progression, (as necessary for any imbalances in baseline variables) when examining between-group differences in the MMRCDS and CDS scores across the multiple study time points (i.e., baseline, 8, 16, 24 weeks). Finally, we will compute the effect sizes and Reliability Change Index⁶⁸ to assess practical and clinical significance of the differences in the primary and secondary outcomes. The GLM model will generate an effect size estimate, which can also be calculated by hand ($d = \text{Mean}_{\text{change score CBT group}} - \text{Mean}_{\text{change score control group}} / \text{SD}_{\text{pooled}}$). Cohen⁶⁹ utilizes cutoffs of 0.2 for a small effect, 0.5 a medium effect, and 0.8 for a large effect.

6.3.2 Aim 2

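### Section 6.4's remedy for data judged not random is maximum likelihood with no dropout model, which on the same variables needs the same missing-at-random condition as the imputation it replaces

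*Combined protocol and SAP*

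**What the plan says.** Section 6.4 sets out four things.

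- Order: "The analyses will initially focus on the study completers to estimate the effect of the brief behavioral intervention", that is, in patients "who completed the protocol as intended without imposing assumptions about missing data".
- Intention-to-treat: "We will also use the intention-to-treat principle with all randomized subjects", "conducting sensitivity analyses to explore how various assumptions about missing data" and completer/non-completer differences affect the results.
- First branch: "If data appear to be missing at random, we will employ multiple imputation methods".
- Second branch, if it is found that "patients do not complete the study because of disease worsening, suggesting missing data are not random, we will employ maximum likelihood estimation", applied to the incomplete data under the biostatistician's direction.

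Two other places bear on this. Section 5.4.2 states: "The post study review of the electronic health record (EHR) will include information on disease progression". Section 6.3.1 (Aim 1) uses longitudinal mixed models in part "to control for demographic and clinical factors, such as disease progression, (as necessary for any imbalances in baseline variables". Section 5.6.1 expects worsening and deaths over the course of the study.

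**The concern.** The second branch is triggered when the missing-at-random condition is thought to fail, yet the method it names needs that condition. No selection, pattern-mixture, shared-parameter or joint dropout model appears in section 6. Dropout from disease worsening is the case the plan itself foresees. In that case a reader could take the maximum likelihood result as a not-at-random check when it is not one, while the analysis that would serve as such a check is left unnamed.

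The completers wording is a second, smaller problem. Read as the effect in all randomized patients, a completers comparison assumes that completion is unrelated to outcome given arm and the modelled covariates. The word used to place it first gives an order of work; it does not settle whether completers or intention-to-treat carries the primary conclusion.

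**Working it through.** **The plan's own figure.** Section 6.2: 200 completers, 0.40 SD, two-sided 0.05, 80% power. Power = Φ(0.40·√(100/2) − 1.96) = Φ(2.83 − 1.96) = 0.807; by the noncentral t, 0.804. It reproduces and is not disputed.

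**Step 1: the two branches.** The full likelihood of the observed data is ∫ f(y_obs, y_mis | θ) · f(dropout | y_obs, y_mis, ψ) dy_mis. Maximum likelihood without a dropout model drops the second factor. That is valid when dropout does not depend on y_mis given what is observed (and θ and ψ are distinct), which is missing at random. Standard multiple imputation draws y_mis from a model fitted to the observed data and relies on the same condition. On the same variables, the switch changes the computation and leaves the assumption as it was.

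**Step 2: numerical check.** One million simulated patients, 16% missing in each arm, true effect −0.40 SD (negative favours the intervention). Assumed: baseline to week-8 correlation 0.5; dropout log-odds 1.2 per SD of its driver.

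| Dropout driven by | Completers, baseline-adjusted | Maximum likelihood | Multiple imputation |
|---|---|---|---|
| Unseen week-8 score, same in both arms | −0.40 | −0.40 | −0.40 |
| Unseen week-8 score, controls only | −0.28 | −0.28 | −0.28 |
| Unseen week-8 score, intervention only | −0.52 | −0.52 | −0.52 |
| Recorded worsening, controls only, variable omitted | −0.32 | −0.32 | −0.32 |

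In the last row, maximum likelihood with the worsening variable included returns −0.40. When dropout depends on the baseline score in one arm only, which is missing at random, unadjusted completers give −0.49 while both other methods give −0.40. So a completers analysis is not assumption-free.

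**Step 3: at trial size.** 110 per arm (section 5.5), correlation 0.5, dropout log-odds 0.7 to 1.5 per SD of the unseen score in both arms. The loss splits are assumed. Bias and type I error are under no true effect, 4,000 trials each.

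| Loss, control/intervention | Bias (SD) | Type I error |
|---|---|---|
| 16%/16% | 0.000 to 0.001 | 4.3% to 4.8% |
| 12%/20% | −0.037 to −0.067 | 5.8% to 8.1% |
| 20%/12% | +0.037 to +0.066 | 6.5% to 8.7% |
| 16%/26% | −0.048 to −0.081 | 6.7% to 10.5% |
| 26%/16% | +0.047 to +0.078 | 6.7% to 10.0% |

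Over six scenarios with a true effect of 0.40, imputation and maximum likelihood differed on average by at most 0.0008 SD. A four-visit likelihood model gave the week-8 result exactly when dropouts did not return, and removed at most about 0.007 SD of bias when 30% did.

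**Step 4: recorded progression.** Assumed: 30% progress before week 8, progression adds 0.8 SD, dropout log-odds 1.5 to 2.5. A true 0.40 reads 0.43 to 0.44 (16%/26%) or 0.36 to 0.38 (26%/16%) without progression, and 0.40 at both splits with it as an auxiliary variable.

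**Step 5: tipping point.** Suppose missing intervention patients are worse than predicted by delta and missing controls are not. The estimate falls by (fraction lost) × delta. With the standard error held at its observed-data value, the smallest significant estimate is t·√(2(1 − r²)/n), r = 0.5.

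- About 16% loss (the single-group pilot rate in section 6.2): 18 of 110 lost, fraction 0.164, n = 92. Threshold = 1.973·√(1.5/92) = 0.252. Delta = (0.40 − 0.252)/0.164 = 0.90 SD, or (0.30 − 0.252)/0.164 = 0.29 SD.
- 9% loss (220 to 200): 10 of 110 lost, fraction 0.091, n = 100. Threshold = 1.972·√(1.5/100) = 0.242. Delta = (0.40 − 0.242)/0.091 = 1.74 SD, or (0.30 − 0.242)/0.091 = 0.64 SD.

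For r from 0.3 to 0.7 at 16% loss, these run 0.75 to 1.17 SD (estimate 0.40) and 0.14 to 0.56 SD (estimate 0.30).

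**The case against.** Five points can fairly be made for the plan.

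- **Sensitivity analyses are promised.** They are, and they could include a not-at-random method. None is named, and the only method tied to not-random data is maximum likelihood. Delta adjustment is one reasonable choice among several.
- **Disease worsening is not by itself not-at-random.** This stands. Step 4 shows that recorded, dated progression can bring such dropout under missing at random. A reader might infer that the switch can never remove bias, or must give the same answer as imputation. The documents do not support that: section 6.4 lists variables for neither method, and the equality holds only on the same variables.
- **Section 6.3.1 contemplates progression as a covariate.** It does, in a sentence that ambiguously ties it to baseline imbalance, although progression during the study is not a baseline variable. It would go too far to say the clause excludes progression from a dropout-related model; equally, nothing links it to dropout.
- **The completers analysis has its own target.** Section 6.4 aims it at patients who completed the protocol and then adds intention-to-treat. A reader might infer that the trial rests on completers alone, or that missed sessions exclude intervention patients only. The first is not stated. The second depends on a definition of completion that the plan does not give, and the remote delivery and baseline reset in section 5.5.2 would limit it.
- **The size is assumed.** True. The pilot's 16% comes from one group over six weeks. The team's early-stage nursing trial in section 1.2 lost 2 of 120, about 2%. Neither gives loss by arm for this population. The simulations are for a continuous outcome; the ordinal MMRCDS, tested by Wilcoxon and then GEE, is not modelled.

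**Conclusion.** The point holds as a defect in the stated rule and should be fixed. With no dropout model named, the remedy for not-random data has no stated advantage over imputation on the same variables and cannot serve as a not-at-random check. The claim that the completers analysis imposes no assumption is wrong if its result is read as the randomized effect, and the primary analysis set is not identified.

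The practical effect is unknown. A reader might infer that the trial's result will be biased towards the intervention; the documents do not support a direction or a size. On the assumed inputs, bias is about 0 when loss is equal and works alike in both arms, and 0.04 to 0.08 SD either way at the unequal losses tried. That range is not a bound: in Step 2, outcome-driven dropout confined to one arm gave 0.12 SD. An observed effect of 0.40 SD would be fairly robust (delta 0.90 SD at 16% loss, 1.74 SD at 9%, r = 0.5). An effect of 0.30 SD would be less so (0.29 and 0.64 SD). Neither named method would show which case applies.

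**What to change.** 1. State that the primary week-8 comparison includes all randomized patients in their assigned arm and uses every observed week-8 score regardless of session attendance, under missing at random (multiple imputation or a likelihood-based mixed model). Include the baseline score. Where progression is dated before week 8, use it as an auxiliary variable. Make the completers analysis supportive, define completion, and delete the claim that it imposes no missing-data assumption.
2. Replace maximum likelihood as the not-at-random remedy with a prespecified not-at-random sensitivity analysis, for example delta-adjusted multiple imputation with delta varied by arm and a tipping-point table for week-8 MMRCDS and CDS.
3. Report missing week-8 data and deaths by arm. How deaths enter the estimand is a separate decision.

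The cost is SAP wording and analysis code. Section 5.4.2 does not mention a progression date, so the record-review form may need that field. The estimate may move either way and the interval may widen slightly. Enrolment and patient assessments are unchanged.

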6.5 Potential Problems, Alternative Strategies and Benchmarks for Success

The potential problems and alternative strategies that we considered in developing this study proposal pertain to the selection of interventionists, length of treatment, and nature of the control group. Specifically, we recognize that patients with advanced lung cancer may benefit from meeting with clinical psychologists and/or social workers with trained expertise in behavioral medicine. Although increasing contact with such clinicians may enhance the robustness of the intervention, we are responding to the present challenges that exist in meeting the psychosocial and symptom management needs of patients with cancer. Access to supportive care for oncology patients is limited not only by the inadequate number of mental health and palliative care providers, but also by insufficient training of existing clinicians with respect to empirically-supported techniques, such as cognitive-behavioral approaches.⁴³ In our national survey of community oncologists, a majority reported that they lack access to mental health providers for referrals.^{70,71} We therefore decided to administer the point-of-care dyspnea intervention, delivered by trained oncology nurses, as we observed that this approach was feasible and preferable to patients with advanced lung cancer. Similarly, prior studies of comprehensive dyspnea management interventions include numerous visits with multiple medical providers across several months.^{37,46} Given the disease burden of the patient populations in the proposed study, we chose to keep the intervention brief, delivered in tandem with existing outpatient appointments. Despite this short-time frame of the targeted behavioral intervention, we nonetheless observed a large effect size for self-reported dyspnea over time in our pilot study.²³ Interventions that can be integrated within the flow of care that are minimally resource intensive yet effective have greater potential for broad adoption and implementation across diverse cancer care settings. Finally, we elected to conduct a RCT with a usual care control group rather than employ alternate experimental methods, such as a wait-list crossover or staggered treatment design, because of the shortened life expectancy of the study population. We also considered, but ultimately did not include, an attention-matched control group given the lack of an alternative, evidence-based psychosocial comparator as well as potential ethical considerations of asking patients with advanced disease to meet with a clinician for some sort of "sham" treatment. Moreover, no data suggest that attention alone would influence dyspnea. Otherwise, we will not limit access to usual care but rather examine the effects of the behavioral intervention above and beyond usual care.

Benchmarks for success in the proposed study will not simply include a replication of our successful pilot study showing significant effects of the brief behavioral intervention on dyspnea management. We also aim to increase the generalizability and reach of the intervention by training oncology nurses and including a second study site. Also, we will consider clinically meaningful

improvements in quality of life (i.e., ≥ 5 point change on FACT-L) and a Reliability Change Index ≥ 1.96 for the outcomes as other markers for success. If we do not achieve these benchmarks, we will utilize qualitative methods to gather feedback from the relevant stakeholders (i.e., patients, nurse interventionists, etc.) to ascertain ways to modify the intervention content and/or delivery in order to maximize its effectiveness and adoption in multiple cancer care settings.

